8.3 Objective 3: Enhance disease surveillance and outbreak detection

All data generated by ePOCT+ will be sent to a central sever based at IHI. Data will be visualized through the medAL-outbreak dashboard made available to district health authorities using the key M&E and HMIS indicators they will have chosen. To enhance disease surveillance, targeted microbiological testing will complement the syndromic surveillance data generated automatically by ePOCT+ in HFs. This microbiological testing may take place during Phases 1 and 2 in 6 to 8 sentinel HFs (3 to 4 per site) on children presenting with at least one of three syndromes (significant respiratory disease, gastro-intestinal disease or non-specific fever). In response to the spatiotemporal analyses,

at a later stage of the surveillance study, we may expand surveillance sample collection beyond the sentinel sites using a mobile surveillance team. Rapid tests will be used on site and appropriate microbiological tests (PCR and serologies) will be performed at the research laboratories of NIMR-Mbeya and IHI-Ifakara/Bagamoyo once every other week.

To be able to perform these specific investigations for surveillance purposes, from which sick children will not benefit directly for the present acute episode (only indirectly when they attend for another episode and the algorithm has been improved in the meantime), caregivers of targeted children will be asked by the HCW to sign a separate written consent form allowing biological specimens to be collected. Caregivers and children will be asked if they agree to provide an additional blood, stool, urine or nasopharyngeal sample for research and surveillance purposes, and be provided a paper-based participant information and sample collection form providing sufficient information for caregivers to make an informed decision about their participation in this sub-study. All children participating in the surveillance sample collection will undergo the full written consent process (same as children participating in other sub-studies).

Thresholds for the detection of abnormalities in the data and for alerts for potential epidemics will be integrated in the medAL-outbreak system. Results will be discussed with the Epidemiology section of the MoH under the Directorate of Preventive Services (DPS), including the necessity for additional confirmatory tests at the Geneva Centre for Emerging Viral Diseases. This will allow health authorities to investigate if the cause of abnormal trends in the data is due to a real local epidemic or another reason. For example, a sudden increase in malaria cases could be due to a problem with the quality of the batch of malaria RDTs used. If the cause of the abnormality is not obvious, more in-depth investigations will be undertaken, such as performing clinical evaluations by an experienced physician or using pathogen rapid test (such as a Dengue or typhoid RDT) on site or other targeted lab tests at the research laboratory of IHI in Bagamoyo or NIMR in Mbeya (such as multiplex PCR with a tropical fever panel). These more in-depth data will also feed into the ML analyses and improve prediction capacity of children' clinical outcome. The clinical management algorithm will be modified temporarily, if necessary, according to the clinical experts.

8.3.1 Training and feedback of the CHMT on medAL-outbreak

After finalizing the list of health indicators with the person in charge of M&E and HMIS at the district health office, the medAL-outbreak dashboard will be installed on her or his PC. She or he will be trained on how to use the tool and interpret trends in the indicators for decision-making. Her or his feedback on the interface will be solicited and the dashboard will be modified, if necessary, to ensure optimal user experience. Regular discussion between the site investigator and the district team will take place throughout the study to modify or further improve the medAL-outbreak tool.

8.4 Objective 4: Enhance M&E and supportive supervision and mentorship

A similar process will be undertaken to ensure optimal use of the medAL-monitor tool. Individuals who normally conduct supervision visits to HFs will be trained on how to use and interpret the information displayed on the dashboards. HCWs and facility in-charges will also receive training on how to monitor their clinical practices at the individual and facility levels, perform self-audits, and build internal capacity and culture of quality improvement. User feedback will be solicited throughout the project and the interface improved.

8.5 Objective 5: Create a supportive environment for the use of clinical decision support algorithms and disease surveillance tools

8.5.1 Implementation research

During Phases 1 and 2, qualitative studies will be undertaken to assess facilitating factors and barriers to ePOCT+ deployment. HCWs, caregivers, community members and district health managers will be interviewed to assess the perception and acceptability of ePOCT+ and related tools.

Sustainability of the intervention will be evaluated by assessing the level of local human capacities that will have been reached at the end of the study in terms of: 1) clinical competencies by HCWs; 2) clinical algorithm creation by medical experts; 3) software and IT infrastructure maintenance by computer scientists; 4) disease surveillance and outbreak detection by health authorities and; 5) ML analysis by data scientists. These capacities will be enhanced by specific professional training programs and exchanges organized by the different institutions involved in the DYNAMIC project, as well as the University of Dar es Salaam for ML.

Finally, costing analyses will be performed using ML on the data collected throughout the study, assigning a cost to each procedure performed during consultations, as well as to transportation to the HF or to the hospitalization of the child. An ecological assessment of the intervention will also be performed to calculate the carbon footprint or carbon-saving of the intervention.

8.5.2 Stakeholder involvement and community sensitization

The objectives of the study and the way in which it will be conducted have already been discussed with the ICT and M&E Technical Working Group of the Ministry of Health in Tanzania and Child Health unit in the Reproductive and Child Health section of the Department of Preventive Services at the Ministry of Health. The ICT and M&E section of the President's Office Regional Administration and Local Government (PO-RALG) have been informed of the study and their support for the study obtained in principle.

In addition, the District Medical Officers and the CHMT members of the study districts in Ifakara TC, Kilombero DC and Mbeya DC have been contacted, informed of the study and provided support in the initial selection of study facilities by providing some information relevant for the study inclusion and exclusion process. Both have indicated willingness to support the study and work together once all approvals are obtained from respective authorities.

A Tanzanian stakeholder group will be established. It will contribute to the content of key documents and give feedback on the planned activities. If needed, international experts can be invited at certain time points. The stakeholders group might evolve along time but the initial composition will include Child health experts, Member/ leaders of the Pediatric association in Tanzania, Influential people (elders or religious), ICT/ ML experts in Tanzania, political leader at local communities, and CHMT or RHMT representative.

Members of the community will also be involved throughout the study. Meetings with community leaders will be held in convenient locations to encourage participation. In initial study introduction meetings, community leaders will be informed of the study and asked to disseminate the information to their communities. Subsequently, wider community meetings will be held to solicit feedback about the intervention throughout the study period. Lastly, focus group discussions will allow community members to formally participate in the study.

8.5.3 Development of frameworks for the future scale-up of the e-POCT+ intervention

During the last year of the DYNAMIC project, we will develop for the Tanzanian national and district health authorities, as the ultimate owners and users of ePOCT+ and its data, the necessary tools for further national scale-up. These tools will include but are not limited to:

- An optimized version of the software allowing health authorities to modify the e-algorithms without the help of software programmers whenever they need (MedAL-Creator). This software application will allow clinical experts to program, maintain and update any type of algorithm aimed at guiding HCWs during a patient consultation, whatever the age or medical condition. It will also include a feature to deploy or export a new version of the algorithm into all tablets located at the HF. Through an intuitive interface, the user will be able to draw the medical algorithm by dragging and dropping some predefined elements such as exposures, signs, symptoms and diagnostic tests.
- A manual for local experts on the evidence-based path that needs to be followed to adapt and update the algorithm's medical content.
- A document on the best practices for the application of ML to clinical big data.
- To be able to ensure maintenance of the MedAL-Creator open-source software in the long term, Unisanté is presently considering creating a non-profit foundation linked to Unisanté that would provide services at a very low price for low-income countries or public entities, with the aim of reaching the largest possible number of patients with this public good.
- To the extent possible, interoperability guidelines will be developed for the prevailing eHealth tools with which ePOCT+ could be integrated. Examples include, but are not limited to, aggregation of patient level data from ePOCT+ for automated reporting into the DHIS2 platform, or linkage of ePOCT+ to the registration module of an electronic medical records system so that information from patient encounters managed using ePOCT+ can be stored in the patients' medical record.
- Support to health authorities willing to develop implementation guidelines that take into account the facilitators and barriers discovered during the project will be provided upon request.

9 LABORATORY PROCEDURES

9.1 Specimen collection and management

Trained HF routine staff will collect venous blood samples by standard venipuncture from the right or left antebrachium into pre-labeled vacutainer tubes containing EDTA and serum separator tubes. The total volume (for clinical management and surveillance) will not exceed 2.4 ml/kg per patient weight (maximum 15 ml), as recommended by KEMRI and WHO guidelines, of which a maximum of 1 ml/kg (maximum 6 ml) will be used for surveillance purposes (WHO 2013). Two nasopharyngeal samples will be collected by gently rubbing a sterile, synthetic swab on the patient's nasal mucosa for 2-5 seconds. For stool samples, the subject will be provided a pre-labeled container in which to collect the sample and instructions on how to collect uncontaminated samples.

All collected samples will be stored temporarily at the HF in a fridge and then transferred in batches in a cooler box with ice packs to the reference research laboratories for storage in an ultralow (-20°C or -80°C) freezer until analysis. In the two reference research laboratories in Mbeya and Bagamoyo, a testing strategy combining several levels of basic and advanced diagnostic tests, specific to the syndrome presented by the children, will be applied on the samples (that will be pooled whenever possible to save testing resources).

All Tanzanian and Swiss-based implementing partners/personnel handling specimens and involved in their transport will be trained prior to conducting the procedures. Training will be provided at each site by the laboratory coordinator and supported by site investigators under the supervision of the country coordinator. Only trained HF staff and project personnel will have access to the specimens. To address participant privacy and confidentiality, all biological samples will be labeled with a unique identification code assigned to each enrolled sampled child, and then logged in a register (sample log/map or database). Results of the surveillance laboratory investigations, which will be available 2

to 3 weeks after the initial consultation, will be communicated back to health workers by the research team from IHI or NIMR. Health workers will forward the results to the caretakers.

The majority of the laboratory analyses will be conducted at research laboratories in Tanzania at reference research laboratories in Mbeya or Ifakara in accordance with the procedures described below. In rare cases, Material Transfer Agreements (MTA) will be filled by all partners prior to any sample transfer from Tanzania to the Centre for Viral Emerging Diseases in Geneva, Switzerland. When shipping samples between Tanzania and the Centre for Emerging Viral Diseases in Geneva, the shipper will obtain all necessary documentation and permits from the appropriate regulatory authorities and follow all safety and International Air Transport Association (IATA) guidelines. The shipper will notify the approved couriers for transport in approved secured shippers and provide the recipient with the air bill/tracking number(s) and itemized shipping log.

Biobanks: All specimens will be securely stored in locked and temperature monitored ultralow freezers in Mbeya and Ifakara research laboratories for up to 15 years after project completion. The specimen database will be password-protected, and personal identifying information kept in a secure manner and maintained by the surveillance and information management team, and not share to a third part. Access will be restricted to project personnel only for surveillance data analysis.

9.2 Serology to characterize exposure to viral and/or bacterial pathogens

Commercial and established standardized serological assays for known agents, both bacterial and viral will be used to screen children with syndromes of interest. When appropriate, serological assays will be performed on-site, and for advanced characterization the samples will be analyzed at the reference research laboratories in Mbeya or Ifakara and at Geneva Centre for Emerging Viral Diseases.

9.3 Viral detection and discovery

Virus detection in collected samples will be performed using a combination of multiplex PCR such as BioFilm Array and advanced analyses such as high throughput sequencing (HTS) and full genome sequencing to detect known and discover novel viruses from different sample types. All personnel handling these samples will follow biosafety guidelines and perform viral nucleic acid extraction and molecular detection protocols in a required biosafety level facility at Mbeya or Ifakara. Virus targeted are of potential pandemic or epidemic significance and those for which public and preventive measures (i.e. vaccination, education) exist.

9.4 Molecular detection of bacterial pathogens

Appropriate microbiological tests and multiplex PCR targeting conserved genes will be used to identify the full range of bacterial pathogens and to identify new bacterial agents in samples from children with diseases of unknown origin where the viral infections have been ruled out.

10 STATISTICAL METHODS

10.1 Sample size calculations

Throughout the study, non-inferiority in clinical cure will be defined as a risk difference of $<30\%$ in the proportion of clinical failures while superiority in clinical cure will be defined as a decrease of $\geq30\%$ in the proportion of clinical failures. Superiority regarding resources (whenever medicines prescribed or diagnostic tests ordered by HCWs or time spent to perform a consultation) will be defined as a decreased need of $\geq25\%$.

10.1.1 Cluster-randomized controlled study (Phase 1)

For the cluster-randomized study in Phase 1, the primary analysis will evaluate whether the use of ePOCT+ for case management of sick children in PHC facilities 1) results in similar clinical cure at day 7 (non-inferiority analysis), as compared to routine care and 2) decreased antibiotic prescriptions (superiority analysis) at the initial consultation. The sample size was calculated for testing the non-inferiority of the clinical cure outcome, which will require a much larger sample size due to the rareness of the event. In addition, the testing of differences in antibiotic prescription is conditional on satisfying non-inferiority in the clinical outcome. Assuming a failure rate of 3% in the control arm (corresponding to a 97% clinical success rate), based on previous studies, the acceptable non-inferiority margin will be a risk ratio of 1.3. This corresponds to the upper bound of the difference in failure rate not exceeding 0.9% if the control group failure rate is 3%. We utilized a fixed risk ratio rather than an absolute risk difference to protect against potential unexpected event rates (Head et al. 2012).

We assumed a cluster size of 900 patients and an intraclass correlation coefficient of 0.002 in the clinical outcome based on similar studies. To have 80% power to detect a risk ratio 1.3, for a one-sided hypothesis test at alpha of 0.025, we would require 19 clusters and 17,100 patients per arm (total patients n=37,620 assuming 10% loss to follow-up), rounded to a total of 40 HFs and 40'000 patients. However, due to uncertainty regarding the assumptions of the sample size calculation and to capture a wider more representative range of conditions, we will continue recruitment for Phase 1 for a minimum of 6 months. Due to lower enrollment than initially anticipated, an independent statistician will use the clinical failure outcome data from the control arm, and projected number of patients enrolled after all health facilities have enrolled patients for a minimum of 6 months to recalculate the sample size. If the sample size recalculation does not have sufficient power to meet the study objectives, the study may be extended, or the number of health facilities increased. To avoid implementation bias, the clinical failure proportion in the control arm will not be shared to the study team.

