| Statistical considerations | 
Throughout the study, non-inferiority in clinical cure will be defined as a risk difference of <30% in the proportion of clinical failures while superiority in clinical cure will be defined as a decrease of $\geq 30\%$ in the proportion of clinical failures. Superiority regarding resources (whenever medicines prescribed or diagnostic tests ordered by HCWs or time spent to perform a consultation) will be defined as a decreased need of $\geq 25\%$.
 |

| | |
|----------------------------|---|
| | 
For the cluster-randomized study in Phase 1, the primary analysis will evaluate whether the use of ePOCT+ for case management of sick children in PHC facilities results in 1) decreased antibiotic prescriptions at the initial consultation (superiority analysis) and 2) similar clinical cure at day 7 (non-inferiority analysis), compared to routine care. The sample size was calculated for testing the non-inferiority of the clinical cure outcome, which will require a much larger sample size due to the rareness of the event. In addition, the testing of differences in antibiotic prescription is conditional on satisfying non-inferiority in the clinical outcome. Assuming a cure rate of 97% in the control arm based on previous studies, the acceptable absolute non-inferiority margin will thus be one third of 3% (100%-97%), thus 1%. We assumed a cluster size of 900 patients and an intraclass correlation coefficient of 0.002 in the clinical outcome based on similar studies. To have 80% power to detect this difference of $\geq 1\%$, for a one-sided hypothesis test at alpha of 0.025, we would require 19 clusters and 17,100 patients per arm (total patients n=37,620 assuming 10% loss to follow-up), rounded to a total of 40 HFs and 40'000 patients.
 
For Phase 2, sample sizes for the randomized sub-studies, aimed at evaluating the effect of a modification in the algorithm leading to a potential positive impact, will be calculated following the same general principles. In Phase 2, we expect that an average of 200 children per month per HF will be managed using ePOCT+, which corresponds to around 500,000 consultations over 2 years in the 100 HFs selected on predefined criteria.
 |

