The second-generation algorithm called ePOCT, ‘electronic Point of Care Tests’, was based on a thorough review of the evidence and the existing national and international guidelines on the diagnosis and management of sick children (Keitel et al. 2017). In addition to symptoms and signs, it made use of several POC tests to help detect children with severe infections requiring hospital-based treatment and/or children with serious bacterial infection. The interactive electronic decision tree supported a systematic assessment of the child and the consideration of several health problems at once (**Figure 1**). It increased the ability to detect children with severe disease, which was further supported by pulse-oximetry and POC hemoglobin testing (to screen for severe anemia, a strong predictor of bacteremia). POC inflammatory host biomarkers, such as CRP, detected children in need for antibiotic treatment. Diagnostic and triage tests were only performed in patient groups with sufficient pre-test disease probability (which is indicated by the algorithm). Integrating

[figure not shown]
such POCTs is important since clinical signs alone lack accuracy in detecting children with severe infection and/or in need for antibiotic treatment.

Figure 1: ePOCT addresses the major challenges in pediatric case management.

[figure not shown]
The safety of ePOCT was assessed among over 3,000 febrile children aged 2 months to 5 years through a randomized trial in Dar es Salaam, Tanzania in 2014-2016 (Keitel et al. 2017); this was an essential first step since ePOCT contained important upgrades compared to IMCI. The use of ePOCT resulted in higher clinical cure (98%) as compared to ALMANACH (96%) and routine care (95%). The algorithm also further reduced antibiotic prescription to 11%, as compared to 30% with the use of ALMANACH and 95% in routine care (Figure 2).

Figure 2. Percentage of antibiotic prescription for children under-five with fever when managed per e-POCT and ALMANACH algorithms, and per routine care in Dar es salaam, Tanzania.

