Analyses will follow CONSORT guidelines (Schulz et al. 2010, Piaggio et al. 2012) and intention-to-treat (ITT) principles, that is including all participants as randomized. A flowchart will describe the inclusion and follow-up of participants by study arm. Baseline characteristics will be described by study arm with summary statistics such as median and interquartile range or number and percentage; no formal testing between arms will be performed (Pocock et al. 2002). Outcomes will be described by arm using summary statistics. For the non-inferiority comparison between ePOCT+ and the control arm for clinical cure, a CI approach will be used. A figure illustrating the CIs and the non-inferiority margin will be presented. Primary analyses for the non-inferiority comparison will be performed on both the per protocol and ITT sets (Committee for Proprietary Medicinal P 2001). If ePOCT+ is found to be non-inferior to the control in terms of clinical cure rate, then we will assess for superiority using the ITT set. If non-inferiority is established, we will test for significant differences in the co-primary outcome of antibiotic prescription rate. For this outcome, the percentage of patients receiving antibiotics at day 0 will be assessed using multi-level logistic regression model regression with the cluster included as a random effect. Binary secondary outcomes will be evaluated in the same way. All estimates will be reported with 95% confidence intervals (CI).

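### The Phase 1 non-inferiority margin is an absolute 1 percentage point in the synopsis but a risk ratio of 1.3 in section 10.1.1, and both carry the same 19 clusters per arm at 80% power

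*Protocol*

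**What the plan says.** The two margin statements are both in the current protocol text.

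- **Synopsis, Statistical considerations:** "the acceptable absolute non-inferiority margin will thus be one third of 3% (100%-97%), thus 1" (per cent). It continues: "for a one-sided hypothesis test at alpha of 0.025, we would require 19 clusters and 17,100 patients per arm".
- **Section 10.1.1:** "the acceptable non-inferiority margin will be a risk ratio of 1.3", converted there to an upper bound of 0.9% on the failure difference at 3% control failure. The scale is presented as deliberate: "We utilized a fixed risk ratio rather than an absolute risk difference to protect against potential unexpected event rates". The sample size sentence reads "To have 80% power to detect a risk ratio 1.3, for a one-sided hypothesis test at alpha of 0.025, we would require 19 clusters", again with 17,100 patients per arm.
- **Section 10.1, and the opening of the synopsis paragraph:** "Throughout the study, non-inferiority in clinical cure will be defined as a risk difference of" less than 30% in the proportion of failures. That is a relative figure under an absolute label. Read as a relative increase, it agrees with a ratio of 1.3.
- **Section 10.3:** "For the non-inferiority comparison between ePOCT+ and the control arm for clinical cure, a CI approach will be used". It refers to the margin but gives neither its value nor its scale.

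The synopsis and sections 10.1.1 and 10.3 all make the antibiotic comparison conditional on non-inferiority in cure. The SAP supplied covers the medAL-mentor ancillary study and says nothing on the Phase 1 margin.

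**The concern.** An absolute margin and a relative margin are different rules, not two roundings of one rule. Section 10.1.1 rejects the kind of margin that the synopsis sets. Because cure is the gate, the choice of rule decides whether the antibiotic co-primary is tested at all. With two rules in writing, the choice could be made, or appear to have been made, after the data are seen.

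The same sample size is also claimed for both margins from identical inputs, so at least one power statement is unsupported. Section 10.1.1 further asks an independent statistician to recalculate the sample size from control-arm failures, after which the study may be extended or facilities added. That answer depends on the margin and scale used.

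**Working it through.** **Inputs** (identical in the synopsis and section 10.1.1): control failure 3%; 900 patients per cluster; ICC 0.002; one-sided alpha 0.025; power 80%. Allocation is 1:1 (section 3.1). The true difference is not stated; I take equal true rates unless noted.

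Design effect: 1 + (900 - 1) x 0.002 = 2.798. The multiplier is (1.960 + 0.842)^2 = 7.849.

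**Step 1. Reproduce 19 clusters.** For a fixed difference d, patients per arm before clustering are 7.849 x 2 x 0.03 x 0.97 / d^2.

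- d = 0.009: 5,640; x 2.798 = 15,781; / 900 = 17.5 clusters. This gives 18 rounded up, and 19 with one cluster added or with a t distribution on 2(k - 1) degrees of freedom. So 19 is recovered from the 0.9-point difference.

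**Step 2. The same method for the other readings.**

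- d = 0.01: 4,569; x 2.798 = 12,784; / 900 = 14.2 clusters (15, or 16 with the correction).
- Ratio 1.3 on the log scale: 7.849 x 2 x (0.97/0.03) / (ln 1.3)^2 = 7,374; x 2.798 = 20,632; / 900 = 22.9 clusters (23, or 24 with the correction).

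**Step 3. Power at the stated size.** The effective number per arm is 17,100/2.798 = 6,112 at 19 clusters and 18,000/2.798 = 6,433 at 20. Power is Φ(margin/SE - 1.960). For example, 0.9 points at 19 clusters: SE = sqrt(2 x 0.03 x 0.97/6,112) = 0.309 points; 0.9/0.309 = 2.92; power 83.1%. On the log ratio scale, SE = sqrt(2 x (0.97/0.03)/6,112) = 0.103; ln 1.3/0.103 = 2.55; power 72.3%.

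| Rule, 3% failure, equal true rates | 19 clusters, normal / t | 20 clusters, normal / t |
|---|---|---|
| 1-point difference | 90.0% / 88.4% | 91.4% / 90.0% |
| 0.9-point difference | 83.1% / 81.0% | 84.9% / 83.0% |
| Log risk ratio 1.3 | 72.3% / 69.9% | 74.4% / 72.2% |
| Contrast p1 - 1.3 x p0 | 71.0% / 68.7% | 73.2% / 71.0% |

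A beta-binomial simulation (8,000 replicates) gave, at 19 and 20 clusters, 89.5% and 90.6% for 1 point, 82.4% and 84.0% for 0.9 points, and 71.9% and 74.0% for the log ratio.

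The ratio-scale figures depend on the true ratio. By normal approximation at 19 and 20 clusters, a true ratio of 0.99 gives 75.2% and 77.3%; 0.98 gives 78.0% and 80.1%; 0.97 gives 80.6% and 82.6%.

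**Step 4. Can the rules disagree?** Take 20 clusters of 900 per arm, with ICC 0.002 held constant (an assumption). The upper limits are

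- difference: (p1 - p0) + 1.96 x sqrt((p0q0 + p1q1) x 2.798/18,000)
- ratio: (p1/p0) x exp(1.96 x sqrt((q0/p0 + q1/p1) x 2.798/18,000))

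| Observed failure, intervention vs control | Upper limit, difference | 1-point rule | Upper limit, ratio | Ratio 1.3 rule |
|---|---|---|---|---|
| 2.2% vs 2.0% | 0.2 + 1.96 x 0.253 = 0.70 points | passes | 1.10 x exp(1.96 x 0.1205) = 1.39 | fails |
| 5.4% vs 5.0% | 0.4 + 1.96 x 0.391 = 1.17 points | fails | 1.08 x exp(1.96 x 0.0753) = 1.25 | passes |

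**Step 5. Effect on the recalculation.** At 20 clusters with equal true rates (normal approximation), control failure of 2% gives 98% power for 1 point but 57% for the log ratio of 1.3. At 5% the order reverses: 74% against 93%.

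**The case against.** The strongest reply is that this is a synopsis left out of step with a clear body text. The synopsis opens with the relative 30% definition and derives its 1% as a third of the assumed 3%, so the 1% can be read as a rounded conversion. At the planned rate the gap is 0.1 point. If the margin were re-derived as one third of control failure at other rates (a ratio of about 1.33), both examples above would give the same verdict as 1.3. That reading is possible, but the synopsis labels the margin absolute and prints a number, and a fixed 1% applied as written gives the other verdict.

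Other points have partial force:

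- **Plausibility of the rates.** No document reports 2% failure in routine care. Section 1.6 reports routine-care cure of 95% and 92% in earlier studies, so the 5% example has support, although the 95% came from febrile children aged 2 months to 5 years. Section 10.1.1 itself plans for unexpected rates.
- **Unstated method.** A pooled, continuity-corrected test plus one cluster gives 19 for 1 point, but it gives 22 for 0.9 points. No single method tried gives 19 for both.
- **Power is not short on a difference scale.** Under the calculation in Step 3, 19 clusters give at least 80% for either absolute margin. The shortfall arises only if the ratio is tested on its own scale with true rates at or close to equality, and earlier versions of the tool improved cure.
- **Timing and missing documents.** Section 10.3 defers detail to a SAP, and the supplied SAP mentions a separate Phase 1 SAP, which may fix the scale. The supplied SAP also reports preliminary Phase 1 findings, so advice on the recalculation may come after it was done. Neither point removes the conflict in the protocol text.

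**Conclusion.** The concern holds: the protocol is wrong as written and must be corrected. It contains two margins for the gating hypothesis, close at 3% control failure (1.0 against 0.9 points; ratios of 1.33 and 1.30) but capable of opposite verdicts at 2% and 5%. By one consistent method, 19 clusters per arm cannot be the 80%-power requirement for both. The figure matches a fixed 0.9-point difference after a small-sample correction. It is more than the 1-point margin needs (14.2 clusters before correction) and fewer than a ratio-scale test of 1.3 needs with equal true rates (22.9).

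The conflict between margins is plain from the text and rests on no assumption. The power figures assume 3% failure, ICC 0.002, equal clusters of 900 and, except where stated, equal true rates. The ratio-scale shortfall is therefore conditional: it disappears at 19 clusters if the true ratio is about 0.97, and at 20 clusters if it is about 0.98.

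**What to change.** 1. Use one margin in the synopsis and in sections 10.1 and 10.1.1: failure risk ratio below 1.3, for the reason section 10.1.1 already gives. Delete the absolute 1%.
2. In the synopsis and section 10.1, replace the risk-difference wording with a relative increase of less than 30% in the failure proportion.
3. In section 10.3, name the scale of the confidence interval and the value that its upper limit must stay below.
4. State power on that scale, with the method and the true ratio assumed. If the scale is the risk ratio, this is about 71-74% for 20 clusters of 900 per arm with equal true rates (73-74% by normal approximation, 71-72% with t), or 80% with a true ratio of 0.98 (normal approximation). If it is the fixed 0.9-point difference, say so and keep 80%, but then drop the argument for a fixed ratio, because it no longer applies.
5. Have the independent recalculation use the same margin and scale, with the observed ICC and the variation in cluster size. If it has already been done, record which margin and scale it used.

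The cost is wording in the synopsis and sections 10.1, 10.1.1 and 10.3, plus agreement with the Phase 1 SAP. The correction itself requires no extra enrolment. The stated power falls only if the ratio scale is confirmed with equal true rates.
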